11.4 Toxicity Monitoring

Evidence of Toxicity will be monitored closely in all patients. For each arm, treatment will be terminated if Pr(non hematological grade 3 or higher clinically significant study drug related Toxicity >0.3 | data) >0.95. We assume $P_E \sim$ beta (0.3, 0.7). Table 1 shows the simulation of the trial. The treatment will be stopped accrual if the number of patients with clinically significant study drug related toxicities equal to or greater than indicated (i.e., #pts with tox) among the number of patients accrued (i.e., #pts): 2/2, 3/3, 4/5, 5/7, 6/9, 7/11, 8/14, 9/16, 10/19, 11/21, 12/24, 13/27, 14/29, 15/32, 16/35, 17/38, 18/40, 19/43, 20/46, 21/49, 22/52, 23/54, 24/57, 25/60, 26/63, 27/66, 28/69, 29/72, 30/75, 31/77. Multc99 version2.1 has been used for the simulation and boundary computation.

Table 1: OperaSafety Monitorsimulations)		
True	Stop	median
probability	probability	sample size (interquantile)
0.2	0.06	80 (80, 80)
0.25	0.13	80 (80, 80)
0.3	0.28	80 (45, 80)
0.35	0.53	65 (12, 80)

Table 2: Operating characteristics of adaptiverandomization design to compare DAC in twoschedules. Randomly assign 20 patients to eacharm with equal probability before adapting therandomization

	Arm A	Arm B
RR Rate	0.05	0.1
Expected # of Patients	20.1	20.1
Pr(Select)	0.02	0.14
Pr(Select Early)	0.01	0.10
Pr(Stop Early)	0.95	0.73
RR Rate	0.1	0.3
Expected # of Patients	21.5	22.6
Pr(Select)	0.003	0.66
Pr(Select Early)	0.001	0.52
Pr(Stop Early)	0.96	0.07
RR Rate	0.3	0.65
Expected # of Patients	21.7	24
Pr(Select)	0.0002	0.99
Pr(Select Early)	0.0002	0.98
Pr(Stop Early)	0.98	0.0002
RR Rate	0.3	0.3
Expected # of Patients	40.2	40.3
Pr(Select)	0.15	0.15
Pr(Select Early)	0.11	0.12
Pr(Stop Early)	0.21	0.2
RR Rate	0.5	0.6
Expected # of Patients	36.7	43
Pr(Select)	0.03	0.47
Pr(Select Early)	0.03	0.42
Pr(Stop Early)	0.42	0.03

2012-1017 May 24, 2017 Page **25** of **29**

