5.3 Duration of Therapy

In the absence of treatment delays due to clinically significant study drug related adverse events, treatment may continue until one of the following criteria applies:

- Relapsed or clinically significant progressive disease; no response after
 > 3 courses.
 Patients may continue therapy as long as they have stable disease, as long as it is
 determined to be in the best interest of the patient.
- Intercurrent illness that prevents further administration of treatment,
- Patient decides to withdraw from the study, or

- General or specific changes in the patient's condition render the patient unacceptable for further treatment in the judgment of the investigator.
- Up to a total of 24 courses of therapy; about 2 to 3 years.

a. Patients who show no evidence of life-threatening infection or hemorrhage, or less than grade 2 clinically significant drug related non-hematologic toxicity (vomiting included) may be given a subsequent course at the same dose as the previous course. If clinically significant drug-related grade 2 toxicity is observed, the patient must have recovered to grade ≤ 1 before institution of the next course. If patients have clinically significant drug-related grade 3-4 non-hematologic toxicity, they may receive a subsequent course at one reduced dose level after resolution of toxicity to \leq grade 1.

b. Patients with a response (defined under section 10.0) and pre-course counts of granulocytes $>10^{9}/L$ and platelets $>50 \times 10^{9}/L$ who have sustained low counts of granulocytes $<0.5 \times 10^{9}/L$ or a platelet count $<30 \times 10^{9}/L$ for more than 2 consecutive weeks in the current cycle, may receive a subsequent course at 1 dose level reduction. A reduction of 2 dose levels may be considered if the myelosuppression was deemed severe and life threatening by the treating physician, and if it is in the patient's best interest.

c. Patients may receive further courses of therapy not earlier than 4 weeks from the previous course, provided the patient has recovered from myelosuppression considered to be related to chemotherapy. Patients with rapid increase in blasts may start additional therapy before 28 days from start of the previous course.

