d. A minimum of 1 full course (or 4 weeks from the start of therapy) will be required for a patient to be considered as having received an adequate trial to evaluate efficacy. All patients receiving at least one dose of decitabine will be considered evaluable for toxicity. Patients achieving a partial response or with stable disease may continue on therapy until definite evidence of disease progression.

e. Patients who achieve CR or CRi may be treated with additional courses of decitabine every 4-8 weeks or longer if approved by the PI. The dose of decitabine can be adjusted down by one dose level for toxicity (see above). Patients may be taken off study or treated on other programs (e.g. bone marrow transplantation) if this is judged more appropriate for their therapy and overall outcome. Delays of more than 8 weeks to subsequent course may be allowed if determined by the investigatory to be in the best interests of the patient after discussion with the PI and the discussion documented in the patient's medical record. Abnormalities in chemistries including BUN, LDH (lactic dehydrogenase), alkaline phosphatase, magnesium, glucose, phosphorus, calcium and electrolytes will not be reported as adverse events. These are indications of disease process and not of toxicity, therefore clinically insignificant. Delayed recovery in patients post CR is common in MDS and AML not associated with significant clinical complications such as bleeding or infections. Therefore, delayed myelosuppression after a course in CR will be

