11.0 Statistical Considerations

11.1 General description

This is a Phase II open-label, efficacy and toxicity study of two treatment arms (arm A: Decitabine 20mg/m^2 IV daily for 5 days versus arm B: Decitabine 20mg/m^2 IV daily for 10 days) in subjects with AML ≥ 60 or unfit for standard cytotoxic chemotherapy. Patients will be enrolled to evaluate the 2 dose schedules. For both arms, one course will consist of 4 weeks. An adaptive randomization design will be employed to compare the efficacy between the two arms. The primary efficacy outcome is the complete response which is defined as the complete remission (CR) or complete remission with incomplete recovery (CRi) assessed after three cycles. At the end of the trial, we will estimate the probability that one arm is superior to the other. We will also evaluate toxicity on each arm. A maximum of 100 patients will be accrued, at an expected accrual rate of 5 patients per month.

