11.3 Study Design

A maximum of 100 patients will be adaptively randomized into two treatment groups:

Arm A: Decitabine 20mg/m2 IV daily for 5 days

Arm B: Decitabine 20mg/m2 IV daily for 10 days

Patients will be assigned to receive different schedules of Decitabine, using an adaptive procedure that bases assignment probabilities on observed results in preceding patients. At first, 20 patients will be assigned to each arm with equal probability. As efficacy data accrues, patient assignment to the two arms will become unbalanced in favor of the one that has the higher complete response rate (RR). The RR for both arms will be estimated with a 95% CI (similar to Bayesian highest posterior density interval).⁴⁹

Based on previous studies, we expect a RR of about 30% in both arms. Therefore, we assume RR has a prior Beta distribution (0.6, 1.4) with mean 0.3. Let RRa and RRb denote the response rates for arm A and arm B, respectively. Beginning with the 21st patient in each arm and for each subsequent patient, we will compare RRa with RRb, incorporating data from all patients with evaluable response. In order to avoid favoring one arm earlier in a large trial, instead of assigning patients with posterior probability (Pa=Pr(RRa>RRb|data) and Pb=1-Pa), we use the following formula to assign patients:

2012-1017 May 24, 2017 Page **23** of **29**

Aa= $\frac{\sqrt{Pa}}{\sqrt{Pa} + \sqrt{Pb}}$, Ab=1-Aa, where Aa is the probability of assigning patients to arm A, Ab is the

probability of assigning patients to arm B, Pa is the posterior probability that arm A is superior to arm B and Pb is the posterior probability that arm B is superior to arm A.

If at any point during the trial Pr(RRa>RRb|data)>0.95(or <0.05) the schedule A(or B) will be selected as superior. If accruing information gives strong evidence that a RR of 30% or greater is unlikely to be true for any one of the treatment arms (Pr(RRa or RRb>0.3|data)<0.05), assignment to that arm will be stopped. If the maximum of 100 patients is enrolled and evaluated and Pr(RRa>RRb|data)>0.9 (or <0.1), we will declare that arm A(or B) has a higher RR rate than arm B (or A). Otherwise, the trial will be inconclusive. We used simulation (5,000 simulations per scenario) to evaluate the performance of the adaptive randomization procedure under several different scenarios (Table 2). Adaptive Randomization version 4.1 has been used for the simulation. Adaptive Randomization version 4.1 has been used for the simulation.

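### Table 1's chances of stopping for toxicity are those of one arm of 80, the per-arm ceiling; at the arm sizes Table 2 expects, the chance at true toxicity 0.35 is 0.32 to 0.42, not 0.53

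*Combined protocol and SAP*

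**What the plan says.** Section 11.4 closes an arm when the posterior probability that its rate of qualifying toxicity (non-hematological, grade 3 or higher, drug-related) exceeds 0.3 is above 0.95, under a Beta(0.3, 0.7) prior. It lists the matching counts from 2/2 to 31/77 and adds "Table 1 shows the simulation of the trial". Table 1 gives stop probabilities of 0.06, 0.13, 0.28 and 0.53 at true rates 0.20, 0.25, 0.30 and 0.35. Its sample-size column tops out at 80 in every row.

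The trial has two arms. Section 11.1: "A maximum of 100 patients will be accrued, at an expected accrual rate of 5 patients per month". Section 11.3: "At first, 20 patients will be assigned to each arm with equal probability", with adaptive allocation after that. Table 2, also in 11.4, gives the expected patients in arms A and B:

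| Response rates A/B | Arm A | Arm B |
|---|---|---|
| 0.05/0.1 | 20.1 | 20.1 |
| 0.1/0.3 | 21.5 | 22.6 |
| 0.3/0.65 | 21.7 | 24 |
| 0.3/0.3 | 40.2 | 40.3 |
| 0.5/0.6 | 36.7 | 43 |

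The count list sets toxicities "among the number of patients accrued (i.e., #pts". No toxicity window is stated.

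**The concern.** The rule works arm by arm, yet the table offered as the simulation of the trial uses an arm about twice the size expected in the longer scenarios and three to four times the size expected in the others. A rule checked after every patient has more chances to stop in a longer arm, so the larger size raises the stated probabilities. The effect is greatest where the true rate is near or above the 0.3 limit. The 0.35 row is the only printed row above that limit, so it is the one a reader would use to judge whether an over-toxic arm would be closed. At stake is that judgement. Arm B starts at 20 x 10 = 200 mg/m² per course against 20 x 5 = 100 mg/m² in arm A, in older or unfit patients.

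**Working it through.** **Inputs.** Limit 0.3, cut-off 0.95, Beta(0.3, 0.7) prior and the count list (11.4); total of 100 (11.1); 20 per arm before adaptation (11.3); expected arm sizes (Table 2).

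**Step 1: thresholds.** For each n, take the smallest count b(n) with Pr(p > 0.3 | Beta(0.3 + b, 0.7 + n − b)) > 0.95. One toxicity in one patient gives 0.854 (no stop) and two in two gives 0.961 (stop), which matches the first entry, 2/2. All 30 printed pairs are reproduced.

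**Step 2: stop probability.** Let f(n, x) be the probability of having x toxicities after n patients without having stopped, with f(0, 0) = 1. Then

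f(n, x) = (1 − p) f(n − 1, x) + p f(n − 1, x − 1).

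At each n, the mass at x ≥ b(n) is moved to stopped. The stop probability for an arm of N is the total moved by n = N. This is exact and treats each outcome as known at once.

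**Step 3: reproduce Table 1.** With N = 80:

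| True rate | Table 1 | Exact, N = 80 |
|---|---|---|
| 0.20 | 0.06 | 0.067 |
| 0.25 | 0.13 | 0.135 |
| 0.30 | 0.28 | 0.280 |
| 0.35 | 0.53 | 0.528 |

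The quartiles also agree closely. At 0.35 the lower quartile is 12 (printed 12) and the median 68 (printed 65). At 0.30 the lower quartile is 48 (printed 45).

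**Step 4: where 80 comes from.** 100 − 20 = 80. It is reached only if the other arm closes at 20 and this arm runs to the cap.

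**Step 5: the same recursion at other sizes.**

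| True rate | N=20 | N=24 | N=37 | N=40 | N=43 | N=60 | N=80 |
|---|---|---|---|---|---|---|---|
| 0.20 | 0.065 | 0.065 | 0.066 | 0.066 | 0.067 | 0.067 | 0.067 |
| 0.25 | 0.120 | 0.122 | 0.129 | 0.130 | 0.130 | 0.133 | 0.135 |
| 0.30 | 0.203 | 0.211 | 0.239 | 0.241 | 0.245 | 0.264 | 0.280 |
| 0.35 | 0.317 | 0.335 | 0.404 | 0.410 | 0.420 | 0.475 | 0.528 |
| 0.40 | 0.457 | 0.487 | 0.603 | 0.612 | 0.629 | 0.716 | 0.791 |
| 0.50 | 0.745 | 0.787 | 0.909 | 0.916 | 0.929 | 0.974 | 0.992 |

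The low rows barely move because most of their stopping is very early: at 0.20 the first two patients alone contribute 0.2² = 0.04 of the 0.067.

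**Step 6: spread of arm sizes.** The figures above fix N at a mean. Simulating the 11.3 design (3,000 trials per scenario, immediate response, trial ending once an arm is selected or dropped) gives mean arm sizes of 40.1/40.3 at 0.3/0.3 and 36.3/42.3 at 0.5/0.6, close to Table 2. Averaged over the simulated sizes, the stop probability at 0.35 is 0.40 in both arms at 0.3/0.3, and 0.39 (A) and 0.41 (B) at 0.5/0.6. An arm of 70 or more occurred in under 0.2% of runs.

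**The case against.** **Table 1 is right for what it simulates, and its 80s are visible.** Both are true. The arithmetic and the thresholds stand. The table's caption is damaged in the text available here and may name the cohort size. Even so, the body text presents the table as the trial, and no stopping probability is given at the sizes Table 2 expects.

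**Eighty is attainable.** This also stands. Section 11.3 says only that assignment to a futile arm stops, so the other arm could run on. On that reading arms of 79 to 80 do occur: arm sizes of 70 or more appear in about 2% to 7% of runs at 0.3/0.3, depending on whether superiority is still checked once an arm is closed. The average at 0.35 in the two longer scenarios still stays between 0.39 and 0.42. At 0.1/0.3 the change is larger: with superiority still checked, arm B averages 29.8 patients and 0.357. That size does not match Table 2's 22.6, which fits a trial that ends.

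**A reader might infer that the whole table is wrong or that patients are less protected.** Neither follows. At 0.20 and 0.25 the largest change is about 1.5 points (0.120 against 0.135 at N = 20). The rule acts identically on the first 40 patients whether the arm is planned at 40 or 80, and a smaller arm exposes fewer people: at 0.35 the mean number treated is 28.5 with N = 40 and 49.5 with N = 80.

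**A reader might also infer that the count-list denominator makes the rule lax.** Section 5.3(d) gives that reading some support: "All patients receiving at least one dose of decitabine will be considered evaluable for toxicity". The response rule in 11.3, by contrast, works by "incorporating data from all patients with evaluable response". If patients with pending outcomes are counted as toxicity-free, then relative to immediate outcomes stopping can only be delayed or prevented, because the threshold never falls as n rises. But the governing criterion is a posterior given the data, and the literal reading is not the only one. The size rests on an assumed lag. At N = 40, true rate 0.35 and 2.5 patients per arm per month, stopping is 0.37 to 0.39 with a 1-week lag, 0.33 to 0.37 with 2 weeks and 0.27 to 0.33 with 4 weeks, against 0.41. The documents do not establish that the trial would be run this way.

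**Conclusion.** The point holds as a misstatement of operating characteristics. Table 1 describes an arm at its ceiling. At the sizes Table 2 expects, the chance of stopping at true toxicity 0.35 is about 12 points lower in the longer scenarios and about 19 to 21 points lower in the shorter ones. At 0.30 the shortfall is about 4 points and 7 to 8 points. The lower rows can be left as they are in substance.

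This rests on checking after every patient with immediate outcomes, as Table 1 itself does, on toxicity being independent of response, and on Table 2's arm sizes. It is not a defect in the stopping thresholds. The treatment of pending patients is a secondary note: its direction is secure under the literal reading, but its size is not, because the plan states no toxicity window.

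**What to change.** Keep the thresholds. Restate Table 1 at about 20, 40 and 60 patients per arm, label 80 as the per-arm maximum, and add rows at true toxicity 0.40 and 0.50 (N = 40: 0.61 and 0.92; N = 80: 0.79 and 0.99). The values are in the working above, so the change is one table and one sentence. The cost is that the stated chances of stopping at 0.30 and above become less favourable.

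Optional: the sponsor could state the toxicity window and how pending patients count, then simulate that choice at 5 patients per month. One particular rule should not be prescribed: counting events at once while toxicity-free patients wait 4 weeks. With the thresholds unchanged and all events spread evenly over course 1, it raises false stopping at N = 40 from about 0.07 to as much as 0.12 at a true rate of 0.20, and from 0.13 to as much as 0.21 at 0.25. Any choice must also say how later toxicities count, since treatment may run long: "Up to a total of 24 courses of therapy; about 2 to 3 years".

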5.2 Therapy

The initial Decitabine courses should be given at MD Anderson Cancer Center (or Regional Cancer Centers), either as in-patient or as out-patient. Decitabine will be dosed based on actual body weight. However, at the treating physician's discretion an adjusted body weight may be used, if actual body weight is >40% over ideal body weight. Adjusted body weight = ((Actual body weight – Ideal body weight) 0.4) + Ideal body weight. Decitabine may be subsequently administered at any of the Regional Cancer Centers (RCC) or at the patients' local oncologist offices. Patients will be assigned in a selective Bayesian design to one of two treatment arms.

- 1) Decitabine 20 mg/m² IV over approximately 1 hour daily x 5.
- 2) Decitabine 20 mg/m² IV over approximately 1 hour daily x 10.

Start at dose level 0 as shown below. There will be no dose escalation of Decitabine.

Patients will receive one course every 4-8 weeks; however delays of more than 8 weeks may be allowed if determined by the investigator to be in the best interest of the patient after discussion with the PI and the discussion documented in the patient's medical record. Doses may be given as close as 8 hours apart if approved by the PI. If prolonged aplasia and/or a major infection is seen, may decrease 1 dose level after marrow regeneration. This will be rounded to the following daily lower dose (15, 10, 7.5, 5 mg/m²). Otherwise continue at the same dose level every 4-8 weeks depending on recovery of counts and disease status. If persistent disease, start next course regardless of counts. If marrow complete response is achieved with adequate cellularity, start subsequent courses when granulocytes $\geq 0.75 \times 10^9$ /L and platelets $\geq 50 \times 10^9$ /L.

Patients on the 10 day regimen will receive 5 day dosing after achieving CR during consolidation/maintenance. The 5 day dosing may also be initiated in these patients after the first course, if it is thought to be in the best interest of the patient after discussion with the PI and the discussion documented in the patient's medical record. Patients on the 5 day regimen will continue to receive the 5 day regimen after the first course whether in CR or not.

Modifications of dose schedule or dose level other than above are allowed if felt to be in the patients best interest to optimize response or reduce toxicity. These decisions should be documented in the patient's medical record.

	Decitabine mg/m ²	² daily x days

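### The toxicity boundary in 11.4 counts every accrued patient with no observation window, so it stops an over-toxic arm less often and later than Table 1 states

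*Combined protocol and SAP*

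**What the plan says.** Section 11.4 terminates an arm if "Pr(non hematological grade 3 or higher clinically significant study drug related Toxicity >0.3 | data) >0.95", with a Beta(0.3, 0.7) prior. It turns this into a list of limits beginning "2/2, 3/3, 4/5, 5/7, 6/9, 7/11, 8/14", each read as events over patients, and takes the second number "among the number of patients accrued (i.e., #pts"). It names no observation window, no minimum follow-up and no handling of patients whose outcome is still open.

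Section 5.3(d) uses a different population: "All patients receiving at least one dose of decitabine will be considered evaluable for toxicity". That also has no time limit, although treatment may last long: "Up to a total of 24 courses of therapy; about 2 to 3 years".

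The response comparison in 11.3 is worded differently. It uses only patients whose response can be evaluated.

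Section 11.1 gives the two timing facts that bear on delay: accrual "at an expected accrual rate of 5 patients per month", and "For both arms, one course will consist of 4 weeks".

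**The concern.** Beta-binomial monitoring treats every patient in the denominator as a finished observation. With accrued patients as the denominator, each new enrolment lowers the observed toxicity proportion at once, while any toxicity in that patient can appear only later. Enrolment alone can move an arm from stop to continue.

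This is the only toxicity stopping boundary in the plan, and one arm tests a schedule with twice as many treatment days. If the boundary is slower than Table 1 says, more patients are treated on an over-toxic schedule than the protocol's readers were told to expect.

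**Working it through.** **1. The boundary.** After x events in n patients the posterior is Beta(0.3 + x, 0.7 + n − x), and the arm stops when Pr(rate > 0.3) > 0.95. Recomputing the smallest stopping x for each n gives 2 at n = 2, 3 at n = 3–4, 4 at n = 5–6, 5 at n = 7–8, and so on. Each printed pair is the first n at which that count is required, and all 30 pairs match.

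**2. Table 1, outcomes known at once.** Exact patient-by-patient recursion, at most 80 per arm:

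| True rate | Table 1 | Recomputed |
|---|---|---|
| 0.20 | 0.06 | 0.067 |
| 0.25 | 0.13 | 0.135 |
| 0.30 | 0.28 | 0.280 |
| 0.35 | 0.53 | 0.528 |

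At 0.35 the median sample size is 68 (quartiles 12, 80), against 65 (12, 80) in Table 1. A model with no outcome delay therefore reproduces the table.

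**3. A small example.** Three toxicities in three observed patients: Beta(3.3, 0.7) puts 0.989 above 0.3, so the arm stops (3/3). Suppose two more patients had enrolled before the third toxicity was seen and have not been observed. The count reads 3/5. Beta(3.3, 2.7) puts 0.894 above 0.3, the list requires 4/5, and the arm continues. Nothing more is known about toxicity in the second case.

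**4. Effect of delay with the accrued denominator.** Inputs:
- From the documents: 5 patients per month and 4-week courses. Equal allocation gives 5/2 = 2.5 per arm per month.
- Assumed: onset uniform over one course (28/30.4 = 0.92 months) or three (84/30.4 = 2.76 months).

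On average 2.5 × 0.92 = 2.3 or 2.5 × 2.76 = 6.9 patients are inside the window. At a rate of 0.35, with half of their eventual events still to appear, the count is short by about 2.3 × 0.35 × 0.5 = 0.4 or 6.9 × 0.35 × 0.5 = 1.2 events.

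Simulated stopping probabilities, cap 80:

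| True rate | Instant | Accrued, one course | Accrued, three courses |
|---|---|---|---|
| 0.20 | 0.06 | 0.03 | 0.01 |
| 0.30 | 0.27 | 0.21 | 0.13 |
| 0.35 | 0.52 | about 0.47 | about 0.36 |

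Separate simulations at 0.35 gave 0.44–0.48 for one course and 0.36–0.38 for three. In the extreme where all 5 patients per month enter one arm, 0.35 gives 0.41 (one-month window) and 0.25 (three-month window).

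At a true rate of 0.50 with 40 patients per arm, the median number treated is 8 with instant outcomes, 13 over one course and 23 over three.

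**5. Completed-window denominator.** Windows of equal length close in order of treatment start. If the rule is rechecked at each closing, it sees the same sequence of outcomes as the instant model, so the crossing probability at 0.35 returns to about 0.53 for either window. Patients enrolled while waiting still add to exposure: the median sample size is 69 with a one-month window and 74 with three months, against 68.

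At 0.50 with 50 patients per arm, the median is 12 or 17 (one- or three-month window), against 15 or 25 with the accrued denominator.

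**6. The per-arm cap.** Table 1 uses 80 per arm, but the trial maximum is 100 over two arms. At 50 per arm, instant outcomes give 0.447 at 0.35, and the accrued denominator gives 0.369 (one month) or 0.267 (three months).

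**The case against.** **The denominator is not the whole cause.** With a one-course window and one look per accrual, switching to completed windows moves the 0.35 figure only from about 0.46 to 0.48, and the median treated at 0.50 hardly changes. Under that look schedule most of the one-course loss is the delay itself. This stands, and it is why the fix must also recheck as each window closes. Over three courses the denominator matters under either schedule: 0.37 against 0.48 with one look per accrual.

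**The literal reading is harsh.** The governing criterion conditions on data, 5.3(d) requires a dose, and 11.2 stresses timely entry of events. The one-dose definition does remove untreated patients. It does not remove patients dosed but not yet observed, and prompt entry cannot supply outcomes that have not occurred.

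**A missing window also works the other way.** Counting events over many courses raises each patient's cumulative probability of toxicity. The simulations hold that probability fixed, so they isolate the delay. This is a fair limit on the magnitudes.

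**Stronger readings that the documents do not support.** Section 5.2 says of the 10-day arm: "The 5 day dosing may also be initiated in these patients after the first course". A reader might infer that 5-day courses dilute arm B's toxicity count and weaken its check. The rule counts patients, not courses, so a later 5-day course cannot erase an event and can only add one. What remains is attribution: with no window, the arm B count combines toxicity from 10-day and 5-day courses. A reader might also take each printed pair as the last n for its count and conclude that the list contradicts the rule. Read as first n, the list agrees throughout.

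**Conclusion.** The point holds. As worded, 11.4 treats unobserved patients as toxicity-free, and Table 1 describes a rule in which that never happens. At a true rate of 0.35 and a cap of 80, the stated 0.53 becomes about 0.47 if toxicity appears over one course and about 0.36 over three, at 2.5 patients per arm per month with uniform onset. The direction does not depend on those assumptions; the size does, and the documents give neither an onset pattern nor a per-arm accrual rate. At high true rates the arm still stops in most runs, but after more patients. This is a stated operating characteristic that the written rule does not deliver, and it should be corrected.

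**What to change.** In 11.4, replace the accrued denominator with the number of treated patients who have completed a stated toxicity observation window, and count events in those same patients. Counting toxic patients at once but non-toxic patients only after the window would bias the rule towards stopping. State that the rule is rechecked whenever a window closes as well as at each accrual. Reconcile the wording with the one-dose definition in 5.3(d). Rerun Table 1 with that window, 5 patients per month and a per-arm cap consistent with 100 patients in total.

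The sponsor should choose the window. A short one reports sooner but leaves later courses outside the boundary, including later 10-day courses in arm B. A long one covers more treatment but leaves more patients waiting.

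The cost is one wording change and one simulation rerun. There are two drawbacks: an event already seen does not count until that patient's window closes, and toxicity after the window falls outside the boundary. Later toxicity should therefore still be reviewed, and tabulated by arm and by days of drug actually given.
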